7.8.3 Descriptive Endpoint

- Adverse Events collected via Outreach program. Adverse events (Hospitalized High BG and Hospitalized Low BG) collected during Outreach program will be summarized and presented. Adverse event rates in 100 patient years will also be reported. Adverse events will be further stratified by device component (pump, sensor, sensor server, infusion set, infusion set server, reservoir or accessories), age, gender duration of diabetes and years on insulin.
- The difference in estimated A1C ((average sensor glucose + 36.9) / 28.0) from TS feature ON and TS feature OFF [Nathan D, etc. 2008]. Subgroup analysis of A1c data will be performed on demographic cohorts (age, gender, duration of diabetes and years on insulin), and first A1c (less than 7.0%, 7.0-9.0%, greater than 9.0%). This analysis addresses the primary and secondary safety endpoint per conditions of approval in FDA 530G approval letter
- TS Feature Utilization: TS feature utilization will be calculated using the available SG with TS feature 'turned on', divided by the period of MiniMed 530G device use (i.e. 288 * Number of days with TDD > 0 units) * 100.

Validation of correct TS feature activation (i.e., insulin suspension) with fingerstick when available will be provided including:

1. Total number of insulin suspensions from TS feature activations
2. Total number of insulin suspensions which were accompanied by fingerstick glucose. (fingerstick glucose needs to be within 30 minutes from the Threshold Suspend activation or while the TS is active)

3. Total number of insulin suspensions with fingerstick glucose, categorized by three groups: 1) within $\pm 20\%$, 2) above 20% and 3) below 20% from the sensor glucose value. If SMBG is less than 75 mg/dl, 15 mg/dl will be used to determine which group it belongs to.
- Hypoglycemic Event Incidence, duration and percentage of time spent (SG less than or equal to 50 and 70 mg/dL): with and without TS feature ON, with or without fingerstick glucose. A hypoglycemic event is defined by SG less than the defined threshold for at least 20 minutes. Validation of CGM with fingerstick when available will be provided including:
 1. Total number of hypoglycemic events
 2. Total number of hypoglycemic events that were accompanied by fingerstick glucose (fingerstick glucose needs to be within 30 minutes from the Threshold Suspend activation or while the TS is active)

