 3. Total number of hypoglycemic event with fingerstick glucose, categorized by three groups: 1) within $\pm 20\%$, 2) above 20% and 3) below 20% from the sensor glucose value. If SMBG is less than 75 mg/dl, 15 mg/dl will be used to determine which group it belongs to.
 - Hyperglycemic Event Incidence, duration and percentage of time spent (SG greater than or equal to 180, 250, 300, and 400 mg/dL) with and without TS feature ON; with fingerstick or not. A hyperglycemic event is defined by SG greater than the defined threshold for at least 20 minutes. Provision of fingerstick data when available will provide a separate and important reference to CGM data. Validation of CGM with fingerstick when available will be provided including:
 1. Total number of hyperglycemic events
 2. Total number of hyperglycemic events that were accompanied by fingerstick glucose (fingerstick glucose needs to be within 30 minutes from the Threshold Suspend activation or while the TS is active)
 3. Total number of hyperglycemic event with fingerstick glucose, categorized by three groups: 1) within $\pm 20\%$, 2) above 20% and 3) below 20% from the sensor glucose value. If SMBG is less than 75 mg/dl, 15 mg/dl will be used to determine which group it belongs to.
 - Characteristics of patient behavior for each cohort (e.g. Cohort 1-5 below) will be provided. The provision of this data will help to better understand the profile of patients using this device.

Cohort Description:

- Cohort 1: 0-24% TS feature utilization
- Cohort 2: 25-49% TS feature utilization
- Cohort 3: 50-74% TS feature utilization
- Cohort 4: 75-100% TS feature utilization
- Cohort 5: Data from all 530G uploads regardless of TS feature utilization

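### The fingerstick agreement rule takes its 20% from the sensor but its 15 mg/dL switch from the fingerstick, so near SMBG 75 a closer pair can be called a disagreement and a farther pair an agreement.

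*SAP*

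**What the plan says.** In the commercial data evaluation, SAP 7.8.3 checks threshold-suspend activations against fingersticks: "Validation of correct TS feature activation (i.e., insulin suspension) with fingerstick when available will be provided including" three numbered items. The third is "Total number of insulin suspensions with fingerstick glucose, categorized by three groups": within ±20%, above 20%, and "below 20% from the sensor glucose value. If SMBG is less than 75 mg/dl, 15 mg/dl will be used to determine which group" the pair falls in.

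The same item 3 is repeated for hypoglycemic events ("Total number of hypoglycemic event with fingerstick glucose, categorized by three groups") and for hyperglycemic events. Protocol 7.2.3 carries the same rule in all three places. An accompanying fingerstick is one that satisfies this condition: "fingerstick glucose needs to be within 30 minutes from the Threshold Suspend activation or while the TS is active".

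In the hyperglycemic-event item, SAP 7.8.3 also states the role of the fingerstick: "Provision of fingerstick data when available will provide a separate and important reference to CGM data".

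Neither document gives another base for the percentage or a reason for using SG in one half of the rule and SMBG in the other.

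**The concern.** A rule of this kind keeps a constant percentage at higher glucose and a constant mg/dL band at lower glucose. The two should meet at the switch. Here 20% of 75 is 15, so they would meet if both used the same meter. As written, the percentage follows SG and the switch follows SMBG. When SMBG reaches 75, the tolerance jumps from 15 mg/dL to 20% of whatever SG happens to be: down if SG is below 75, up if it is above. At SG 60 it goes from 15 to 12 mg/dL.

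At stake is the meaning of the three counts. They are offered as validation of suspensions and of sensor-defined events, and Protocol 14.1.5 lists false activation as a risk specific to the feature. If a closer pair can count as a disagreement while a farther pair counts as an agreement, the counts do not measure agreement consistently near the switch. Independent reprogramming under SAP section 8 would not reveal this, because the fault is in the specification.

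**Working it through.** **Inputs** (SAP 7.8.3; same in Protocol 7.2.3): 20% of SG; switch at SMBG below 75 mg/dL; absolute band 15 mg/dL. I read 'within' as including the limit.

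**The plan's own figure.** 0.20 × 75 = 15.0 mg/dL, so the absolute band equals the percentage band at 75 on a single meter.

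**Three rules compared.**
- As written: band = 15 if SMBG < 75, otherwise 0.20 × SG.
- All-fingerstick: band = 15 if SMBG < 75, otherwise 0.20 × SMBG.
- All-sensor: band = 15 if SG < 75, otherwise 0.20 × SG.

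**Worked pairs under the written rule.**

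| SG | SMBG | Apart | % of SG | % of SMBG | Band | Group |
|---|---|---|---|---|---|---|
| 62 | 75 | 13 | 21.0 | 17.3 | 12.4 | above |
| 59 | 74 | 15 | 25.4 | 20.3 | 15 | within |
| 90 | 74 | 16 | 17.8 | 21.6 | 15 | below |
| 93 | 75 | 18 | 19.4 | 24.0 | 18.6 | within |

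In each half of the table the disagreement pair is closer than the agreement pair in mg/dL, in percent of SG and in percent of SMBG. If the limit itself is excluded, SG 60 with SMBG 74 (14 apart; 23.3% and 18.9%) replaces the second row and the result stands.

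**Count of inversions.** An inversion is a disagreement pair that is closer than an agreement pair on all three measures. Over whole-number SG and SMBG from 40 to 130:
- As written: 1,366 inversions, involving 30 disagreement pairs.
- All-fingerstick: 0.
- All-sensor: 0.

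**Where the groups differ.**
- Written against all-sensor, SG < 75 and SMBG ≥ 75: 'above' becomes 'within' when 0.20 × SG < SMBG − SG ≤ 15. Since SMBG is at least 75, SG must be at least 60. This gives SG 60–74.
- Written against all-sensor, SG ≥ 75 and SMBG < 75: 'below' becomes 'within' when 15 < SG − SMBG ≤ 0.20 × SG. In whole numbers this gives SG 80–92.
- Written against all-fingerstick, SMBG ≥ 75: the 'above' cut is 1.20 × SG as written and 1/(1 − 0.20) = 1.25 × SG on SMBG. The 'below' cut is 0.80 × SG as written and 1/1.20 = 0.833 × SG on SMBG, so 'below' changes only when SG exceeds 75 × 1.20 = 90.
- Below SG 60 no pair changes under either alternative. At SG 60 only SMBG 75 changes.
- At SG 180–400 the written and all-sensor rules agree on every pair.

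**Illustrative size.** The documents give no SG or SMBG distribution. Assume SMBG = SG × (1 + bias + error), with normal error of SD 15%, rounded to whole mg/dL. At SG 65, 'above' starts at 79 as written, 81 all-sensor and 82 all-fingerstick. With no bias:
- As written: 1 − Φ((78.5/65 − 1)/0.15) = 1 − Φ(1.385) = 8.3%.
- All-sensor: 1 − Φ((80.5/65 − 1)/0.15) = 1 − Φ(1.590) = 5.6%.
- All-fingerstick: 1 − Φ((81.5/65 − 1)/0.15) = 1 − Φ(1.692) = 4.5%.

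With a 10% bias, subtracting 0.10 from each numerator gives 23.6%, 17.8% and 15.3%.

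For SG assumed between 60 and 90, simulation over bias 0–20% and SD 10–30% puts 'above' under the written rule 0.5 to 5.1 points over all-sensor and 1.6 to 18.6 points over all-fingerstick. 'Below' is 0 to 0.8 points over all-sensor and the same as all-fingerstick.

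**The case against.** The strongest reply is that this is a descriptive endpoint with no margin or decision rule, that a percentage of the sensor value is a legitimate definition, and that the affected strip is narrow. All of that stands: for SG 60–74 only one to four whole-number SMBG values per SG change group.

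Four stronger readings are tempting, and the documents do not support them.

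- A reader might infer that only an SMBG percentage can join the two parts. It is the only choice if the switch stays on SMBG, but moving the switch to SG works equally well and also gives no inversions.
- A reader might infer that the mixed base distorts the hyperglycemia list, for example by hiding pairs whose fingerstick lies below the sensor. The written and all-sensor rules are identical there. Any change at SG 180 or more comes from preferring SMBG as denominator, which is a separate choice.
- A reader might infer that most readings around a low suspension are affected. Neither document gives the distribution of SG at suspension or of threshold settings, nothing changes below SG 60, and hypoglycemic events at the 50 mg/dL threshold are untouched if paired with an SG reading from the event itself.
- A reader might equate 'above 20%' with an unneeded suspension. The plan does not make that equation.

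Two further limits hold. The fingerstick is called a reference only in the hyperglycemic-event item. And the plan does not say which SG reading is paired with a fingerstick taken later in a suspension, which could move pairs by more than this boundary does. The content of SAP pages 20–52 was not available to read, so an operational definition there cannot be excluded. Even so, the rule as stated in both documents would need to be reconciled with it.

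**Conclusion.** The point holds in a limited form. The rule in SAP 7.8.3 and Protocol 7.2.3 is internally inconsistent, and its inversions follow from arithmetic alone, with no assumed distribution. Against a one-meter rule, the inconsistency produces too many 'above' pairs at SG about 60–74 with SMBG of 75 or more. Relative to an all-sensor rule, it also produces extra 'below' pairs at SG about 80–92 with SMBG below 75.

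The percentages in the working depend on the assumed error model and SG values and should be read only as a range. No hypothesis test, alpha, power or sample size changes. The correction is worth making because the counts are presented as validation.

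**What to change.** In item 3 of all three lists in SAP 7.8.3, and in the matching items of Protocol 7.2.3, use one meter for both the percentage and the switch. SMBG is preferable: it already carries the switch, and the hyperglycemic-event item treats it as the reference. Suggested rule:

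- 'Within' if |SG − SMBG| is at most 15 mg/dL when SMBG is below 75 mg/dL, or at most 20% of SMBG when SMBG is 75 mg/dL or more.
- Otherwise 'above' if SMBG exceeds SG, and 'below' if SMBG is less than SG.

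Keeping 20% of SG and moving the switch to SG below 75 mg/dL would also be coherent. If SMBG is chosen, note that the hyperglycemia groups will shift because the denominator changes. It would help to state in the same sentence which SG reading is paired with the fingerstick.

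The cost is one phrase in each list and one line of code, with no new data.

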### **2.1.12. CONTOUR® NEXT LINK Blood Glucose Meter (HMS-9740) – FDA approval K110894**

The Contour NEXT LINK RF enabled BG Meter measures a subject's capillary blood glucose level, which is then used to calibrate the pump. The Medtronic MiniMed 530G pump uses the calibration point in the real-time algorithm which calculates the sensor glucose values that are displayed to the subject. In a normal setting, the result of the SMBG reading is transmitted to the pump via radiofrequency (RF) and can be stored in its memory as a glucose calibration point. The pump asks the user every time if the user wants to use the linked meter BG for calibration. If accepted, the glucose value will be stored in the pump's memory as a calibration point.

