#### Designated Training staff will:

- Train subjects on the use of the Medtronic MiniMed 530G insulin pump.
  - Subjects will be instructed to record carbohydrate intake and exercise into the insulin pump as part of the study requirements
- Train subjects on how to upload the pumps as part of study requirements.
  - Uploads of all study pumps into CareLink Clinical should occur every 21 days throughout the study.

- Subjects will receive an automated reminder (e-mail, text, or voice message) twice a month to remind them to upload pumps.
- In addition to the subject 21 day upload requirement, the Investigational Center staff will again upload pump data at the time of the visit.
- Instruct subjects per User Guide to calibrate the 530G pump at least every 12 hours after the second calibration. For best calibration results per User Guide, subjects will be instructed to calibrate 3-4 times, spread throughout the day.
- Instruct subjects to test their blood glucose per User Guide at least 4 times per day
  - Although the pump has multiple safety alarms, it cannot notify the subject if the set is leaking or the insulin has lost its potency. It is essential; therefore, that the subject tests his or her blood glucose levels at least 4 times per day. If the subject's blood glucose is out of range, he/she should check the pump and the infusion set to ensure that the necessary amount of insulin is being delivered.
- Instruct subjects on the use of the Sensor Dislodgement / Suspected Occlusion Subject Diary
  - Subjects will be instructed to record Sensor Dislodgement / Suspected Occlusion occurrences in the Sensor Dislodgement / Suspected Occlusion Subject Diary.
- Discuss sensor wear requirement.
  - Sensors should be worn throughout the course of the study
- Train subjects on the use of CareLink Clinical which includes that this should only be used to upload the study pump and not for data analysis or diabetes management.
- Instruct subjects to contact the Medtronic 24hr HelpLine in the event they experience problems with their study devices.
- In the event of hyperglycemia, urine ketone test strips will be provided by sponsor free of charge to subjects for use.
- Instruct subjects to report all adverse events as soon as possible. This would include any new medical problem or deterioration of an existing medical problem, such as sickness or glycemic problems. If necessary refer subjects to their own providers or an emergency facility for treatment.

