- Total suspend time including manual suspends, times when the subject sets a temporary basal rate of zero, and threshold suspends separately and together during the nighttime, daytime, and 24 hour periods.
- Frequency of repeated threshold suspends with 1) ≤ 15 minutes and 2) ≤ 60 minutes of basal insulin delivery between suspends.
- Repeated threshold suspends with total suspend durations of ≤ 1 hour, 1- ≤ 2 hours, 2- ≤ 4 hours, 4- ≤ 6 hours, etc. Please calculate “total suspend durations” as the sum of the durations of repeated suspensions with 1) ≤ 15 and 2) ≤ 60 minutes between suspends (intervening basal delivery time should not be included).

7.2.4.5 **CGM Metric:**

- CGM Adherence – average sensor-wear per week
- Comparison between CGM data and Glucose Meter data

7.2.4.6 **Device Performance**

- All complaints that are reported via the 24-hour HelpLine will be summarized and reported.

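### The fingersticks used to check sensor glucose can also be its calibration points, so descriptive CGM-meter agreement may be partly built in and biased upward

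*SAP*

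**What the plan says.** SAP 7.8.3 (same text in Protocol 7.2.3) plans three fingerstick checks in the commercial CareLink data: of TS suspensions, of hypoglycemic events and of hyperglycemic events. Each sorts pairs by whether meter and sensor agree within 20%, with a 15 mg/dL limit when the meter reads below 75 mg/dL. A fingerstick counts if it lies no more than 30 minutes from TS activation or falls inside the suspension. The hyperglycemia item gives the rationale: "Provision of fingerstick data when available will provide a separate and important reference to CGM data". For the trial, SAP 7.2.4.5 (Protocol 7.1.6) lists only "Comparison between CGM data and Glucose Meter data", with no method.

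Protocol 2.1.12 says of the linked meter that it "measures a subject's capillary blood glucose level, which is then used to calibrate the pump", and that the pump "uses the calibration point in the real-time algorithm which calculates the sensor glucose values that are displayed to the subject". Use as a calibration is optional: "The pump asks the user every time if the user wants to use the linked meter BG for calibration". Accepted values are stored in the pump as calibration points.

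Protocol 11.3.2 has trial subjects "calibrate the 530G pump at least every 12 hours after the second calibration", and adds that for best results "subjects will be instructed to calibrate 3-4 times, spread throughout the day". It asks for at least 4 blood glucose tests a day and tells subjects to use only the linked meter. Protocol 14.1.7 mentions 4 to 6 tests a day.

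**The concern.** SG is computed partly from meter readings and is then judged against meter readings. If a fingerstick was accepted as a calibration and is paired with a later SG, the sensor is being compared with its own input. If the paired fingerstick was not itself a calibration but earlier calibrations came from the same meter, any systematic error of that meter sits on both sides of the comparison. Both mechanisms push the pair toward agreement.

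What is at stake is the credibility of a safety description. Protocol 14.1.5 names false activation, and failure to activate, as risks specific to TS. The fingerstick check of suspensions is the planned commercial summary that speaks most directly to false activation. Agreement counts that are too high would make wrong suspensions look rarer than they are.

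**Working it through.** The documents give no agreement rate or precision target for these comparisons, so there is no planned figure to reproduce.

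**1. Overlap between calibration and testing (trial instructions).** Inputs from Protocol 11.3.2 and 14.1.7: calibrations at least every 12 hours, so 24/12 = 2 a day at minimum, and 3 to 4 a day recommended; tests 4 to 6 a day.

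- At 4 tests a day: 2/4 = 50%, 3/4 = 75%, 4/4 = 100%.
- At 6 tests a day: 2/6 = 33%, 3/6 = 50%, 4/6 = 67%.

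So 33% to 100% of instructed fingersticks could be calibration points. This describes trial subjects over a whole day. It does not describe commercial users, or fingersticks clustered around a suspension.

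**2. What the pairing rule permits.** The 30-minute window has no direction and the paired SG is not defined. Three situations are possible:

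- The fingerstick comes before the paired SG and was accepted: it helped to produce that SG, so the dependence is direct.
- The fingerstick comes before the paired SG and was declined: only meter error shared with earlier calibrations remains.
- The fingerstick comes after the paired SG: it cannot have shaped that SG, and again only shared meter error remains.

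**3. Direction.** Let S be the sensor value without this calibration, M1 the calibrating reading, M2 an independent reading of equal precision, and SG = w·M1 + (1−w)·S. With independent relative errors of variance s² (sensor) and m² (meter):

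- Var(SG − M1) = (1−w)²(s² + m²)
- Var(SG − M2) = (1−w)²s² + w²m² + m²

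The second exceeds the first by [(1+w²) − (1−w)²]m² = 2w·m². The artefact is therefore upward whenever w > 0, and it vanishes if the meter has no error.

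**4. Illustration of size.** All inputs here are assumptions: meter CV 5% or 8%; sensor CV 15%, 20% or 25%; w from 0 to 0.75; true glucose uniform on 50–90 or 180–320 mg/dL; 400,000 draws. The limit is 15 mg/dL if the meter reads below 75, otherwise 20% of the meter value (the two meet, since 0.20 × 75 = 15).

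| Range, meter CV, sensor CV | w | Agrees with calibrating reading | Agrees with independent reading | Excess (points) |
|---|---|---|---|---|
| High, 8%, 25% | 0 | 55.3% | 55.3% | 0 |
| Low, 5%, 15% | 0.75 | 100.0% | 99.7% | 0.3 |
| Low, 8%, 20% | 0.5 | 95.9% | 90.4% | 5.5 |
| High, 8%, 20% | 0.5 | 93.4% | 86.2% | 7.2 |
| High, 8%, 25% | 0.75 | 99.6% | 90.7% | 8.9 |

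For w from 0.25 to 0.75, the excess runs from 0.3 to 8.9 points over all combinations.

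**5. Shared meter error only.** The paired reading is not a calibration, but sensor and meter carry a common meter bias (low range, sensor CV 15%, meter CV 5%). With bias SD 5%, agreement is 84.39% against the same meter and 82.31% against an unbiased reference: 2.1 points. With bias SD 10% it is 84.67% against 77.04%: 7.6 points.

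**The case against.** **Points that stand.** Calibration is the user's choice for each reading. Commercial uploads go through CareLink Personal, which also takes third-party meters (Protocol 2.1.6), and the calibration habits of commercial users are not given. For a suspension, the natural comparator is the SG that triggered it, and a fingerstick taken afterwards cannot have shaped that value. *Separate* may simply mean another data source; the plan never claims statistical independence. SAP pages 20 to 52 are not readable in the available text, so a rule stated there cannot be ruled out. These points limit the claim to agreement that can be partly built in. They do not remove it, because the readable rule leaves the paired SG open and admits fingersticks taken before activation.

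**Stronger readings that the documents do not support.**

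- A reader might infer that the commercial co-primary endpoints are compromised. SAP 7.8.2 tests them by paired t-tests on SG, TS ON against OFF. No test, data filter or success rule there uses meter agreement.
- A reader might use only the recommended 3 to 4 calibrations against 4 tests and say that 75% to 100% of fingersticks are calibrations. That omits the 12-hourly minimum and the 4 to 6 tests a day, and it carries trial instructions over to commercial users.
- A reader might assume that calibration removes half the sensor error and count the whole gain as false. With a flat 20% limit and normal error with SD 15%, 20% or 25%, 2Φ(0.20/SD) − 1 moves from 82%, 68% or 58% to 99%, 95% or 89%. The halving has no source in the documents, and the flat limit ignores the 15 mg/dL rule. Calibration also genuinely improves SG: in the high range with meter CV 8% and sensor CV 20%, agreement with an independent reading rises from 64.6% at w = 0 to 86.2% at w = 0.5. Only the further 7.2 points are built in.

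**Conclusion.** The concern holds as a limitation of descriptive analyses that the plan should correct. The dependence is documented in Protocol 2.1.12 and its direction is upward. It reaches the agreement groups in SAP 7.8.3, including the check of correct TS activation, and the trial comparison in SAP 7.2.4.5. No hypothesis test is affected.

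The size is not derivable from the documents. About 0 to 9 percentage points is an illustration that rests on the assumed meter and sensor CVs and calibration weight, and it applies to pairs in which the fingerstick was a calibration. For other pairs, shared meter error of the assumed size gives about 2 to 8 points. How far a whole table shifts depends on the calibration share, which is bounded only loosely for the trial and is unknown for the commercial data. The finding also rests on no exclusion being stated in the unreadable SAP pages.

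**What to change.** Amend SAP 7.8.3 and 7.2.4.5, and Protocol 7.2.3 and 7.1.6 to match:

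1. **Define the pair.** For suspensions, compare the SG that triggered the suspension with a fingerstick taken after activation. A prior-SG rule is not enough here: a fingerstick taken before a suspension, paired with a still earlier SG, does not validate that suspension. For hypoglycemic and hyperglycemic events and for the trial CGM-meter comparison, pair each fingerstick with the last SG recorded before it.
2. **Split by calibration status.** Report agreement separately for fingersticks stored as calibration points and for those not stored, where the flag is available. Protocol 2.1.12 shows that the pump stores accepted calibrations; whether the commercial extract carries that information has to be checked. If it does not, say so in the report.
3. **Correct the description.** Replace *separate* with a statement that the linked meter is also the calibration source. The pairing rule removes the direct dependence but leaves shared meter error in place, so this limitation has to be stated as well.

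The cost is a little programming and a check of the commercial extract. Agreement counts may be slightly fewer, because fingersticks taken before activation leave the suspension table, and slightly less favourable. No new data collection is needed and the primary tests do not change.

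### The fingerstick window in the commercial hypo- and hyperglycemic event lists is tied to Threshold Suspend (TS), so events with TS OFF can almost never count as fingerstick-accompanied

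*SAP*

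**What the plan says.** SAP 7.8.3 contains three numbered fingerstick lists, and Protocol 7.2.3 has the same three.

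- **Suspensions.** The list opens with "Validation of correct TS feature activation (i.e., insulin suspension) with fingerstick when available will be provided including". Item 2 is the "Total number of insulin suspensions which were accompanied by fingerstick glucose", and its parenthesis accepts a fingerstick within 30 minutes of the TS activation or at any time TS is active.
- **Hypoglycemic events.** Item 2 is the "Total number of hypoglycemic events that were accompanied by fingerstick glucose (fingerstick glucose needs to be within 30 minutes from the Threshold Suspend activation", followed by the same alternative.
- **Hyperglycemic events.** Item 2 is the "Total number of hyperglycemic events that were accompanied by fingerstick glucose (fingerstick glucose needs to be within 30 minutes from the Threshold Suspend activation", again followed by the same alternative. Item 3 is the "Total number of hyperglycemic event with fingerstick glucose, categorized by three groups" and has no window of its own.

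The two event lists are introduced as a check of the sensor against fingersticks. On the hyperglycemic side the SAP adds: "Provision of fingerstick data when available will provide a separate and important reference to CGM data". The event definition does not refer to TS: "A hyperglycemic event is defined by SG greater than the defined threshold for at least 20 minutes". The hyperglycemic heading asks for results "with and without TS feature ON; with fingerstick or not", and the hypoglycemic heading asks for the same two breakdowns.

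**The concern.** A window that identifies fingersticks belonging to a suspension has been carried over to events that need not involve a suspension. An event with TS OFF has no TS activation to measure 30 minutes from and no period of TS activity around it.

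If the counts are shown separately for TS ON and OFF, the OFF figures will be close to zero because of the rule, and a reader could conclude that users do not test when TS is off. If they are pooled, item 1 counts TS-OFF events that item 2 almost cannot, so fingerstick coverage looks lower than it is and the agreement groups describe a selected subset.

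This matters beyond tidiness because both commercial co-primary endpoints compare sensor glucose with TS ON against TS OFF. In the readable text of SAP 7.8, these lists are the only sensor-versus-fingerstick check that could cover TS-OFF time, and as written they say almost nothing about it.

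**Working it through.** The plan states no expected count, power or error rate for these items, so there is no figure to reproduce. The check is a reading of the rule against the events it is applied to.

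**Inputs.** The window, event definitions and headings are from SAP 7.8.3 and Protocol 7.2.3. The trigger is from Protocol 2.1.1: TS halts insulin delivery when the sensor reading is low.

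**Step 1: the meaning of *active*.** It could mean that insulin is currently suspended, or that the feature is switched on. The suspension list equates TS activation with insulin suspension, and the section elsewhere uses ON or turned on for the switched-on state. Both favour the first reading, but neither settles it.

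**Step 2: apply the window to each kind of event.**

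| Event | *Active* = insulin suspended | *Active* = feature ON |
|---|---|---|
| TS OFF, low or high | Cannot qualify, except close to an ON/OFF switch | Cannot qualify, except close to an ON/OFF switch |
| TS ON, low, with a suspension | Qualifies with a fingerstick near or during the suspension | Qualifies with any fingerstick in that TS-ON period |
| TS ON, low, no suspension | Does not qualify unless another suspension is close by | Qualifies with any fingerstick in that TS-ON period, even one remote from the event |
| TS ON, high | Qualifies only through a fingerstick near or during a low-glucose suspension | Qualifies with any fingerstick in that TS-ON period, even one remote from the event |

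The first row is the same in both columns, so the near-exclusion of TS-OFF events does not depend on the ambiguity. The other rows differ, so the ambiguity does matter for TS-ON events. Only the low that triggers a suspension is handled sensibly under the favoured reading.

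**Step 3: item 3.** It classifies the events with a fingerstick, which are the events item 2 has admitted, so the restriction carries over. Item 3 also does not say at what time the sensor value is taken. That gap is present in all three lists, including the suspension list, where the fingerstick may fall up to 30 minutes from the activation.

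**Step 4: what does not use the window.** Item 1 totals do not, and neither do event incidence, duration, percent time or the two co-primary tests in SAP 7.8.2. The heading's split by fingerstick status would be affected only if it uses the item 2 rule, which the readable text does not say.

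**Step 5: size.** The documents give the cut-offs: two for hypoglycemia (50 and 70 mg/dL) and four for hyperglycemia (180, 250, 300 and 400 mg/dL). They do not give the layout of items 2 and 3 or the share of events with TS OFF. No effect size follows from them.

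**The case against.** **The link to TS may be deliberate, to study glucose after a suspension.** Where the sponsor wants that link, it puts it in the event definition: in the multi-center trial (SAP 7.2.4.3, Protocol 7.1.6) a hyperglycemic event must fall within four hours of TS activation. The commercial definition has no such condition, and the stated purpose is to check the sensor. This objection does not stand.

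**A programmer would read it sensibly.** The readable text offers no event-anchored window to fall back on. Independent reprogramming under SAP section 8 would reproduce the written rule. SAP pages 20 to 52 survive only as page headers, however, so absence can be claimed only for the readable text. That limit stands.

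**It is only descriptive.** This stands. No hypothesis or decision rule uses items 2 and 3.

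**The size is unknown.** This also stands. A reader might infer that half of the item 2 and item 3 counts are empty by rule, or that fingerstick coverage is capped at the share of events with TS ON. The first assumes a table split by TS status, whereas the items ask only for total numbers. The second assumes a coverage ratio that is not planned and a TS-OFF share that is not given. The documents support neither.

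**An event-anchored window is one choice among several.** This is partly right. The allowance around the event is for the sponsor to choose, but the anchor has to exist for TS-OFF events as well.

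**Conclusion.** The point holds for items 2 and 3 of the two event lists, in both documents. Followed as written, the rule nearly excludes TS-OFF events from the fingerstick counts and agreement groups, whichever way *active* is read. This rests on the readable wording and on taking *accompanied* to mean a fingerstick close in time to the event. It allows for a few events near an ON/OFF switch. For TS-ON events the error depends on the reading: too narrow if *active* means suspended, too loose if it means switched on.

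A reader might infer that the commercial comparison of TS ON with TS OFF is itself biased. The documents do not support that, because the co-primary percent-time results do not use the fingerstick window. The window is also suitable for the suspension list. The defect is worth correcting before the tables are relied on, but its reach is descriptive and its size cannot be stated.

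**What to change.** - In item 2 of the hypoglycemic and hyperglycemic lists, define an accompanying fingerstick relative to the glycemic event: from its start to its end, plus an allowance in minutes that the sponsor states. Use the same rule for TS ON and TS OFF.
- Apply that rule to the heading's split by fingerstick status, and say so.
- Keep the TS-activation window for the suspension list only.
- In item 3 of all three lists, compare the fingerstick with the sensor value at the time of the fingerstick.
- Amend SAP 7.8.3 and Protocol 7.2.3 together. Protocol 2.1.6 speaks of the commercial analysis in the past tense; if it has already been run, label the change as post hoc.

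**Cost.** Item 2 changes in 2 lists × 2 documents = 4 sentences, and item 3 in 3 lists × 2 documents = 6 sentences, with one allowance to choose and the matching program change. No new data are needed: SAP 7.8.3.2 already counts fingersticks over all days of device use, whether or not TS is on.
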